5.3 Treatment Assignment Procedures

5.3.1 Randomization Procedures

Stratified randomization will be used to assign qualifying participants to either conventional itraconazole or SUBA-itraconazole and dosed according to HIV status (positive or negative by clinical self-report) (Section 6.2).

Randomization procedures are described in the Manual of Procedures.

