States, Canada and Central/South America (Approximately: 40 Histoplasmosis, 20 Coccidioidomycosis, 20 other endemic mycoses)

Number of Sites: Approximately 20 total sites in US, Canada, and Central/South

America

Study Duration: This study is estimated to be opened for 18 months after initiation (12

month patient accrual, 6 month treatment period).

Subject Each participant will be enrolled in the study for 180 days

Participation

Objectives:

The objectives of this study are to compare PK, tolerance, safety, and efficacy of SUBA-Itraconazole study drug versus conventional itraconazole in a randomized open-label trial followed by a second stage of continuing open-label study drug.

Stage I - Randomized, Open-Label, Parallel Group

Primary Objective

- PK at Day 14
- Tolerability at Day 42

Secondary Objective

- PK at Day 7
- PK at Day 42
- Efficacy by Day 42
- Safety by Day 42
- QOL (including hospital/ICU visits) Assessments by Day 42

Stage II - Open-Label Extension

Primary Objective

- Efficacy by Day 180
- Tolerability by Day 180

Secondary Objective

- Safety by 180
- QOL (including hospital/ICU visits) Assessments by Day 180

Description of Study Design:

[figure not shown]
This is a prospective, multi-center, randomized, open-label parallel arm study involving patients with proven or probable invasive endemic fungal infection to ascertain the pharmacokinetics, safety, efficacy, tolerability and health economics of oral SUBA-itraconazole compared to conventional itraconazole. Patients will receive randomized open-label study drug (SUBA-itraconazole or conventional itraconazole) over a 42 day period and then continue therapy until Day 180 or earlier if Principal Investigator determines discontinuation of therapy is safe. Patients will be stratified based on clinically reported infection with the human immunodeficiency virus (HIV).

The study sample size will be 80 evaluable patients – target enrollment (three groups: approximately 40 histoplasmosis, 20 coccidioidomycosis, 20 other endemic fungal infections).

Estimated Time to Complete Enrollment

12 Months

Schematic of Study Design:

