4 STUDY DESIGN

This is a prospective, multi-center, randomized, open-label parallel arm study involving patients with proven or probable invasive endemic fungal infection to ascertain the pharmacokinetics, safety, efficacy, and tolerability of oral SUBA-itraconazole or itraconazole. Patients will receive randomized open-label study drug (either SUBA-itraconazole 65 mg twice daily or itraconazole 100 mg twice daily) over a 42-day period and then continue on their assigned open-label therapy until day 180.

The study sample size will be 80 evaluable patients – target enrollment to include approximately 40 histoplasmosis, 20 coccidioidomycosis, and 20 other endemic fungal infections.

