5.2 Subject Exclusion Criteria

All subjects meeting any of these listed exclusion criteria at baseline will be excluded from study participation:

- 1. Significant liver dysfunction as evidenced by at least 5 times greater than upper limits of normal baseline ALT, AST, alkaline phosphatase, or total bilirubin.
- 2. Use of an alternative antifungal therapy (IV or oral) for more than 14 days for this infection with the exception of Coccidioidomycosis. Subjects with Coccidioidomycosis who previously received fluconazole therapy for more than 14 days may be included, if in the opinion of the investigator, they are having an inadequate response or, are intolerant of fluconazole (e.g. due to adverse events). Such subjects must washout from fluconazole for 7 days (~5 half-lives of fluconazole) before starting investigational therapy.
- 3. Evidence of CNS infection.
- 4. Unable to take PO medications.
- 5. Female subjects who are lactating or pregnant.

- 6. Female subjects should be:
 - a) Postmenopausal for 1 year,
 - b) Post-hysterectomy or bilateral oophorectomy,
 - c) If of child bearing potential have a negative β-HCG at screening and using highly effective method of birth control throughout course of study or remain abstinent for duration of study.
- 7. Male subjects with female partner(s) of child-bearing potential, must agree to use a medically acceptable method of contraception during the study. If their partner is pregnant, males must agree to use a condom; if their partner is of child-bearing potential, their partner must additionally be using one of the following methods: hormonal contraception, intra-uterine device, diaphragm, or cervical cap. Spermicides alone are not an acceptable method of contraception. No sperm donations for 90 days post last dose of study therapy.
- 8. Documented intolerance, allergy or hypersensitivity to an azole.
- 9. Inability to comply with study treatment, study visits, and study procedures.
- 10. Known history of congestive cardiac failure on medical treatment, fungal endocarditis, or other causes of ventricular dysfunction that may outweigh the benefit of itraconazole.
- 11. Patients with active TB
- 12. Concurrent use of astemizole, rifampin/rifampicin, rifabutin, ergot alkaloids, long acting barbiturates, carbamazepine, pimozide, quinidine, neostigmine, terfenadine, ketoconazole, valproic acid, or St. John's wort in the 5 days prior to first administration of study drug.

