10.2 Sample Size Considerations

The study will randomize 80 adults infected with one of the endemic mycoses living in the United States, Canada and Central/South America (40 Histo, 20 Cocci, 20 other endemic mycoses). This sample size provides adequate power (77%) to reject the null hypothesis of equal pharmacokinetic means when the population mean difference is $\mu 1$ - $\mu 2$ = 231.7 - 291.7 = -60.0 with standard deviations of 94.0 and 101.8 for the study groups, and with a significance level (alpha) of 0.050 using a two-sided two-sample unequal-variance t-test.

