10.3 Study Outcomes

Stage I- Randomized Open-Label, Parallel Group

Primary Endpoints

- 1. Pharmacokinetic superiority at Day 14
 - a) Inter- and intra- patient variability: Time to attain therapeutic plasma concentrations of itraconazole (> 500 mcg/L)
 - b) Interpatient variability as calculated by co-efficient of variation

Trough (pre-morning dose) sample will be collected at Days 14 and 42. Using validated LC-MS/MS methods, blood samples will be analyzed to quantify plasma concentrations of itraconazole and hydroxyitraconazole.

Participants should arrive to the trial site having **not** taken their morning dose of study drug.

Note: site investigators are discouraged from drawing independent PK laboratories to check itraconazole levels outside of the designated timepoints (Day 14)

2. Tolerability - ability to remain on study drug at Day 42 with less than a 7-day interruption of therapy

Secondary Endpoints

- PK at day 7 plasma concentrations of itraconazole- (comparative trough, steady state plasma itraconazole concentrations of SUBA-itraconazole 65mg capsules with food to itraconazole 100mg capsules with food over 7 days)
- 2. PK at day 42 plasma concentrations of itraconazole- (comparative trough, steady state plasma itraconazole concentrations of SUBA-itraconazole 65mg capsules with food to itraconazole 100mg capsules with food over 42 days)
- 3. Efficacy: clinical outcomes (time to relief of fungal signs and symptoms) at days 14, 28, and 42
- 4. Safety- defined as: adverse events that occurred in each study arm by Day 42
- 5. Tolerability ability to remain on study drug at Days 14 & 28
- 6. Days of Hospitalization and ICU stays at Day 42
- 7. Other health economic endpoints:
 - 1. Number of unscheduled procedures (i.e., labs, scans, etc.) at Day 42
 - 2. Total number of capsules taken at Day 42
 - 3. SF-20 (QOL) assessments at Day 42

Stage II- Open-Label, Extension

Primary Endpoint

- 1. Efficacy- Free from proven or probable invasive endemic fungal infection at Day 180
- 2. Tolerability- ability to stay on study drugs at Days 43 180.

Secondary Endpoints

- 1. Safety- Adverse events that occurred in each study arm between Days 43 180 or end of therapy
- 2. Days of Hospitalization (Days 1 180) defined as days of hospitalization and ICU stays from randomization to Day 180 or end of therapy)

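### Recruitment is planned by mycosis group, but the Day 180 efficacy test ignores it and adjusts only if an imbalance is seen; prespecify a mycosis-stratified comparison.

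*Combined protocol and SAP*

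**What the plan says.** - **Recruitment.** Section 4 gives the sample as 80 evaluable patients, "target enrollment to include approximately 40 histoplasmosis, 20 coccidioidomycosis, and 20 other endemic fungal infections". The Protocol Summary and Section 10.2 repeat the split.
- **Randomization.** Section 5.3.1 states: "Stratified randomization will be used to assign qualifying participants to either conventional itraconazole or SUBA-itraconazole and dosed according to HIV status". The Protocol Summary also names HIV alone. For the rest, "Randomization procedures are described in the Manual of Procedures", and that manual is not among the documents.
- **Eligibility by mycosis.** Section 5.2, item 2, limits other antifungal treatment for the infection to 14 days, with one exception. Coccidioidomycosis patients with longer fluconazole treatment may enter if the investigator judges that "they are having an inadequate response or, are intolerant of fluconazole". Section 5.1 lists six genera, so the third recruitment group can hold four of them.
- **Endpoint.** The first Stage II primary endpoint in Section 10.3 is "Efficacy- Free from proven or probable invasive endemic fungal infection at Day 180". Stage I has a secondary efficacy endpoint, time to relief of signs and symptoms.
- **Analysis.** Section 10.1 names t-tests and chi-square tests, with non-parametric or Fisher alternatives, and carries them over to the secondary and Stage II outcomes. If the arms differ on measured baseline characteristics, which the section regards as unlikely, linear or logistic regression adjusts for whatever differences are observed. Mycosis is not named, and no list of covariates or criterion for imbalance is given.

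**The concern.** Mycosis group is known at entry, and the sponsor already recruits by it. The protocol gives reasons to expect the groups to respond differently. Only coccidioidomycosis patients can enter after inadequate response to, or intolerance of, a long fluconazole course. Section 2.1 also says that treatment length depends on the infection and that azole activity differs between organisms.

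A small group of 20 can fall unevenly between two arms of 40. The pooled efficacy difference then contains part of the difference between mycoses. Section 10.1 leaves it to be decided, once the data are in hand, whether this counts as an imbalance and which covariates enter the model. In an open-label trial that is discretion over a primary efficacy comparison which one sentence could remove.

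**Working it through.** **Inputs from the documents.** "The study will randomize 80 adults infected with one of the endemic mycoses" (Section 10.2); groups of about 40/20/20 (Section 4); HIV the only named stratification factor (Section 5.3.1).

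**Assumptions.** The allocation ratio is not stated; 1:1, or 40 per arm, is assumed. Allocation is treated as unrelated to mycosis. If HIV status and mycosis are associated, stratifying by HIV would balance mycosis in part, but the documents do not quantify this. Success rates by mycosis are not given and are assumed below.

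**1. The plan's own figure.** Section 10.2 states 77% power for the pharmacokinetic comparison. With 40 per arm:
- SE = √(94.0²/40 + 101.8²/40) = 21.91
- noncentrality = 60.0/21.91 = 2.739, with 77.5 Welch degrees of freedom
- two-sided power at 0.05 = 77.2%

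The figure reproduces, which supports 40 per arm. No power is stated for Day 180 efficacy.

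**2. How often a small group splits unevenly.** The number of coccidioidomycosis patients in one arm is hypergeometric: P(k) = C(20,k)·C(60,40−k)/C(80,40). Its SD is √(40 × 20/80 × 60/80 × 40/79) = 1.95 patients.

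| Coccidioidomycosis split | Probability of this or worse |
|---|---|
| 12:8 | 44% |
| 13:7 | 20% |
| 14:6 | 6.9% |

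From the joint distribution of all three groups, at least one of the two small groups splits 13:7 or worse with probability 34%.

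**3. What a split does to the unadjusted difference.** With no drug effect, shift = Σ (share in arm A − share in arm B) × success rate. Take 17/13/10 against 23/7/10 (histoplasmosis/coccidioidomycosis/other):
- at 90/50/80%: (6/40) × (90 − 50) = 6.0 points
- at 90/60/80%: (6/40) × (90 − 60) = 4.5 points

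**4. How likely such a shift is.** Summing over every possible split:

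| Assumed success rates | P(shift ≥ 4.5 points) | P(shift ≥ 6 points) | Median shift |
|---|---|---|---|
| 90/50/80% | 25% | 12% | 2.5 points |
| 90/60/80% | 12% | 3.6% | 2 points |
| 80/70/80% | below 0.01% | 0 | 0.5 points |
| equal in all groups | 0 | 0 | 0 |

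**5. Scale against sampling error.**
- At 90/50/80% the pooled rate is 77.5%, and the SE of the difference is √(2 × 0.775 × 0.225/40) = 9.3 points. Using only variation within mycosis groups it is √[(2/40) × (0.5 × 0.09 + 0.25 × 0.25 + 0.25 × 0.16)] = 8.6 points.
- At 90/60/80% the pooled rate is 80%, and the SE is √(2 × 0.80 × 0.20/40) = 8.9 points. Within groups it is √[(2/40) × (0.5 × 0.09 + 0.25 × 0.24 + 0.25 × 0.16)] = 8.5 points.

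The illustrated shifts are therefore 6.0/9.3 = 0.64 and 4.5/8.9 = 0.50 of one SE.

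**6. Error rates by simulation (200,000 trials per case).** With no drug effect, the type I error of the pooled chi-square test over all splits is about 5%. For a 25-point difference in every mycosis group, with the rates above in the better arm, a Mantel-Haenszel test stratified by mycosis raises power from about 65–67% to 70–71%. If all groups have the same rate, the two tests perform almost alike.

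**The case against.** **The plan already has a remedy.** Section 10.1 allows regression adjusted for observed baseline differences and extends this to Stage II. Mycosis is a measured baseline characteristic, so a visible 13:7 split could be handled there. It would be wrong to infer that the plan has no answer to imbalance. What remains is that the remedy depends on the data, names no covariate and sets no threshold. It is also framed for an unusual event, whereas the chance in step 2 is about one in three.

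**Chance imbalance is not bias.** This stands. A reader might infer that randomizing by HIV alone makes the efficacy test invalid. It does not, because the unadjusted test allows for this source of error on average.

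**The size is assumed.** This also stands. A reader might take a shift of 4.5 to 6 points as a property of this trial, but the documents give no success rate for any mycosis. Nor does the 34% belong to that shift. A 13:7 split in the other group, offset in histoplasmosis, moves the difference by only (6/40) × (90 − 80) = 1.5 points at the assumed rates. The probabilities that go with the shift are those in step 4.

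**Scope.** The only power statement is for pharmacokinetics in a Phase IIb trial of 80. That limits the weight of the point, but Day 180 efficacy is still named as a Stage II primary endpoint.

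**Changing the randomization has a price.** Six strata with small blocks, in an open-label trial at about 20 sites, would leave sparse strata and make assignments easier to predict. This is a fair reason not to insist on it.

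**Conclusion.** The point holds as a recommendation to improve the analysis, not as a fault in validity. The protocol recruits by mycosis, names only HIV as a stratification factor, and compares Day 180 efficacy without a mycosis term unless an imbalance is noticed. Imbalance of 13:7 or worse in at least one small group has a 34% chance, given 1:1 allocation and no association between HIV and mycosis.

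The effect on the efficacy difference depends wholly on how far the mycoses differ. It is zero if they respond alike and negligible with a 10-point coccidioidomycosis gap. With the assumed 30- or 40-point gap between histoplasmosis and coccidioidomycosis, a shift of 4.5 points or more has a 12% or 25% chance. The lasting costs are some lost precision and an adjustment model chosen after the data are seen.

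A reader might go further and conclude that the randomization must be redone by mycosis. The documents do not support that: the Manual of Procedures may add detail that cannot be checked here, and a stratified analysis removes most of the shift without touching the allocation.

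**What to change.** In Section 10.1, state in advance that the Stage I and Stage II efficacy comparisons are stratified by mycosis group (histoplasmosis, coccidioidomycosis, other). Use Mantel-Haenszel for proportions, and mycosis group as a stratum in the time-to-relief analysis. For these comparisons this replaces adjustment only when an imbalance is observed.

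The cost is about one sentence. The factor is already collected at baseline, no new randomization list is needed, and the change remains possible after enrollment has begun. If the mycoses respond alike, almost nothing is lost.

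Adding mycosis to the randomization strata is optional. The gain in balance has to be weighed against sparse strata, incomplete blocks and more predictable assignments.

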5.3.2 Reasons for Withdrawal

A study subject may be discontinued from participation in the study for the following reasons:

- Any clinical adverse event (AE)
- Withdrawn Consent
- Protocol Violation (e.g., violation of any exclusion criteria)
- Lost to Follow-Up

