5.3.3 Handling of Withdrawals

If a subject is withdrawn prior to the end the study, the reason for withdrawal will be documented and entered into the eCRF and if patient is willing to return to be assessed, the End of Treatment (Day 180) assessments will be completed. Documentation of withdrawal in the source documents should include a distinction between participant withdrawal from the study medication regimen and withdrawal from the study itself. In the former case case, the study medication is stopped, but the participant, if willing, continues with study visit assessments; in the latter, study medication and study visit assessments are discontinued.

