8.5 Reporting Procedures

8.5.1 Serious Adverse Events

AEs will be followed until resolution even if this extends beyond the study-reporting period. Resolution of an AE is defined as the return to pretreatment status or stabilization of the condition with the expectation that it will remain chronic.

Any AE that meets a protocol-defined serious criterion must be submitted immediately (within 24 hours of site awareness) on an SAE form (located in the Manual of Procedures) to the MSG Coordinating Center at the University of Alabama in Birmingham.

Contact:

[name]

Mycoses Study Group Administrator
University of Alabama at Birmingham, Infectious Diseases Division
[name]
[name]
[contact]
[contact]
Email [contact]

Other supporting documentation of the event should be provided immediately or as soon as possible.

The Study Principal Investigator will be notified of the SAE by the MSG Coordinating Center and will review and assess the SAE for regulatory reporting and potential impact on study subject safety and protocol conduct.

At any time after completion of the study, if the investigator becomes aware of an SAE that is suspected as being related to study product, the investigator will report the event to the MSG Coordinating Center who will notify Mayne Pharma.

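### Sections 5.3.2 and 5.3.3 let a site end scheduled follow-up for any adverse event or protocol violation, and no text says these patients stay in follow-up to Day 180

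*Combined protocol and SAP*

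**What the plan says.** Section 5.3.2 introduces its list with "A study subject may be discontinued from participation in the study for the following reasons". The four reasons are "Any clinical adverse event (AE"), withdrawn consent, "Protocol Violation (e.g., violation of any exclusion criteria"), and loss to follow-up. The object of the sentence is participation in the study; study drug is not mentioned.

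Section 5.3.3 describes two routes. On withdrawal from the drug regimen, "the study medication is stopped, but the participant, if willing, continues with study visit assessments". On withdrawal from the study, "in the latter, study medication and study visit assessments are discontinued". The separation is a documentation requirement: the source record "should include a distinction between participant withdrawal from the study medication regimen and withdrawal from the study itself". The same section offers a withdrawn patient who is willing to return the End of Treatment (Day 180) assessments, without saying when they take place.

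Section 6.3 allows dose changes or cessation at the investigator's discretion and names drug-related toxicities for which reduction or cessation is considered. It is silent on follow-up afterwards. Section 8.5.1 adds that "AEs will be followed until resolution even if this extends beyond the study-reporting period".

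Section 10.3 makes freedom from proven or probable infection at Day 180 a Stage II primary endpoint.

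**The concern.** A list of reasons for leaving the study normally contains events that make follow-up impossible or unwanted, such as withdrawn consent or lost contact. This list also contains two reasons that leave the patient reachable. An adverse event is itself an outcome, and the decision to end participation because of one is made by investigators who know the treatment arm. If exits of this kind differ between arms, later comparisons rest on patients selected by how they fared on drug.

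The endpoint most exposed is infection status at Day 180. New adverse events after study exit are also exposed, because no visit remains at which they would be collected. Adverse events recorded before exit are less exposed, since they are followed to resolution.

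**Working it through.** **The plan's own figure.** The only design figure is the 77% power in Section 10.2, for a difference of 60.0, standard deviations of 94.0 and 101.8, and a two-sided unequal-variance t-test at 0.05. Assume 1:1 allocation, which is not stated, so 40 per arm. The standard error is √(94.0²/40 + 101.8²/40) = √(220.9 + 259.1) = 21.9, and 60.0/21.9 = 2.74. The noncentral t distribution then gives 77.2%. The figure reproduces. It concerns the pharmacokinetic comparison and is not in dispute. Section 10.2 randomizes 80 and Section 4 calls for 80 evaluable, so the plan carries no allowance for loss.

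**The texts side by side.** The question is whether any text keeps a patient with an adverse event or a violation in scheduled follow-up.

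- Section 5.3.2: names both as reasons for ending participation. It does not direct them to the drug-only route.
- Section 5.3.3: defines both routes and their consequences. It does not say which reasons lead to which route.
- Section 6.3: provides for stopping drug. It says nothing about visits afterwards and nothing about protocol violations.
- Section 8.5.1: follows adverse events that have been reported. It creates no visit for detecting new ones.
- Section 5.3.3, End of Treatment assessment: optional and untimed. Done at exit on, say, Day 30, it falls 180 − 30 = 150 days before the endpoint and gives no Day 180 status.

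No text answers the question, so a site that ends visits after an adverse event of any grade is within the protocol.

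**Assumed illustration of missing outcomes.** Take 40 per arm, study exits of 10% and 20%, and no exiting patient returning.

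- Missing Day 180 outcomes: 0.10 × 40 = 4 and 0.20 × 40 = 8.
- If 80% of observed patients succeed in each arm, the bounds from counting all missing as failure to counting all as success are 0.80 × 0.90 = 72% to 72% + 10% = 82% in the first arm, and 0.80 × 0.80 = 64% to 64% + 20% = 84% in the second.
- The difference (second minus first) can then lie anywhere from 64 − 82 = −18 to 84 − 72 = +12 percentage points.

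**Assumed illustration of direction.** Suppose true success is 80% in both arms, exits are again 10% and 20%, and exiting patients are left out of the analysis. Section 10 states no rule for missing Day 180 outcomes, so this is one possibility among several. Observed success is (0.80 − w × s)/(1 − w), where w is the exit rate and s the success rate among those who exit.

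| s | First arm (w = 0.10) | Second arm (w = 0.20) | False gap |
|---|---|---|---|
| 40% | 0.76/0.90 = 84.4% | 0.72/0.80 = 90.0% | 5.6 points |
| 60% | 0.74/0.90 = 82.2% | 0.68/0.80 = 85.0% | 2.8 points |

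The arm with more exits looks better. These rates show a mechanism; they do not predict what this trial will see.

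**The case against.** The strongest reply is that Sections 5.3.2 and 5.3.3 should be read together. Section 5.3.2 is permissive, Section 5.3.3 uses withdrawal for both routes, and the list may feed either. Section 6.3 with the drug-only route already lets a patient with serious related toxicity stop drug and keep attending. All of this stands, and it shows that the protocol allows good practice. It does not show that the protocol asks for it: the choice of route is left to the site, after the event, with the arm known.

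A reader might infer that an exiting patient has no later laboratory tests, adverse event review or outcome. The documents do not support that. A willing patient is offered the End of Treatment assessments, and the Day 180 column of Appendix A includes chemistry, adverse events, hospital days and mycology. The defect is that the assessment is optional and untimed.

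A reader might also see a contradiction with Section 8.5.1. There is none; that section limits the harm, and the gap is confined to new events after exit.

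A further inference is that removing ineligible patients breaks the randomized comparison. Section 5.3.2 concerns participation and does not exclude anyone from the analysis.

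Two other points lessen the stakes. The Stage II safety and hospitalization endpoints run to Day 180 or end of therapy, so some later loss follows from their definition. Stopping drug for an adverse event before Day 42 is itself information for the Stage I tolerability endpoint, so that endpoint is not lost.

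**Conclusion.** The point holds as a gap in the text. The protocol permits outcome-dependent ending of scheduled follow-up and nowhere says that patients with an adverse event or a violation remain in it. The consequence is concentrated in Day 180 infection status, which has no end-of-therapy cut-off, and in new adverse events after study exit.

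It would go too far to say that the protocol lacks the distinction between stopping drug and leaving the study, or that it abandons all follow-up; Section 5.3.3 contradicts both.

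The size is unknown because the documents give no withdrawal rate. The 4 and 8 missing outcomes, the bounds and the false gaps of 2.8 to 5.6 points rest on assumed exit and success rates, 1:1 allocation and no patient returning; the gaps also assume that missing patients are left out. This is a cheap improvement worth making, not a flaw that invalidates the design.

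**What to change.** Reconcile Sections 5.3.2, 5.3.3 and 6.3 as follows.

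- State that an adverse event or a protocol violation does not by itself end follow-up, and that willing patients keep the scheduled visits to Day 180 whether or not they are on study drug.
- Limit withdrawal from the study to withdrawn consent and loss to follow-up.
- Time the post-withdrawal outcome assessment at Day 180, so that it measures the Stage II endpoint.

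The criteria for stopping study drug are for the sponsor to set and to align across these sections; none is proposed here.

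The cost is a wording amendment and some visits made by patients off drug. Those visits are already in Appendix A, and Section 5.3.3 already provides for attendance off drug.
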